### Pre Incision:

- The patient is prepped and draped in a sterile fashion.
- The incision is marked and the templates are used to mark where the internal receiver/stimulator should be placed.

### Surgical Procedure:

- IV steroids may be administered at the discretion of the surgeon as part of standard medical practices. Middle ear steroids or Healon are not recommended for use within this surgical procedure.
- The incision is made and a palva or similar flap is raised to the external auditory canal.
- A pocket is created under the temporal/parietal periosteum to insert the internal device.
- A trough is drilled from the well to the mastoid for the electrode to lie within.
- A mastoidectomy is then drilled with cortical overhangs, followed by the facial recess.
- Once the facial recess is opened, the lip of the round window is drilled away to expose the round window membrane.
- The internal device is secured and the ground electrode is placed under the temporalis periosteum.

#### A) Specific Round Window Considerations

- Suction is not to be used over the opened round window.
- The electrode is secured prior to its insertion into the cochlea, to facilitate stabilization and orientation of the contacts towards the modiolus.
- A straight incision is to be made in the round window membrane with a 22-gauge hypodermic needle, pick or blade.

#### B) Specific Cochleostomy Considerations

- Suction is not to be used at the cochleostomy site.
- The electrode is secured prior to its insertion into the cochlea to facilitate stabilization and orientation of the contacts towards the modiolus.
- The otic capsule is slowly saucerized using a 1mm diamond burr. The lumen will appear as a bluish or faint gray hue.
- The endosteum is opened using a 0.2mm right angle hook.

#### Electrode Insertion:

- The Cochlear Nucleus CI422 Electrode is inserted using a smooth, single stroke insertion.
- The electrode is held by the AOS forceps in a parallel fashion. Sharp forceps or an electrode claw are not recommended for use, as they may pinch the active portion of the array.
- The tip of the electrode is guided towards the round window or cochleostomy site by the handle/wing and AOS forceps. The handle/wing is positioned inferiorly during electrode insertion to ensure the electrodes are modiolar facing.
- The electrode is advanced slowly (between 30 to 45 seconds) to limit intracochlear trauma and perilymph displacement. The white markers located at 20mm and 25mm on the array provide a guide of the insertion depth.
- The electrode is inserted to the first point of resistance.
- Once the electrode has been inserted, the cochleostomy site or round window and facial recess is packed.

- If the implant's magnet is still in place, tissue damage may occur if the recipient is exposed to MRI. Once the magnet is surgically removed, the metal in the cochlear implant will affect the quality of the MRI. Image shadowing may extend as far as 6 cm from the implant, thereby resulting in loss of diagnostic information in the vicinity of the implant.
- If you need additional information about removal of the magnet, please contact Cochlear Americas.

1.0 Data Analyses

1.1 Study Population

Any subject in whom the Cochlear Nucleus CI422 cochlear implant is attempted to be implanted under this protocol will comprise the intention-to-treat population (ITT). The primary efficacy and safety endpoints will be evaluated with the ITT population. A tipping point sensitivity analysis will be conducted by the methods described in the missing data section to address any missing data.

The effectiveness analyses will also be done on the completed cases (CC) population; treated subjects who had follow-up of the primary endpoint at the protocol prescribed time. A supportive analysis of the primary endpoint will be done in the CC population. Additional analyses will be examined only in the CC population.

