#### **4.1.1 Inclusion Criteria**

1. Eighteen years of age or older at the time of implantation
2. Moderate low frequency thresholds up to and including 1000 Hz, severe to profound high frequency (above 3000 Hz) sensorineural hearing loss.
3. Minimum of 30 days experience with appropriately fit bilateral amplification, fit using the standardized NAL fitting method described in the *Fitting and Use of Hearing Aids* section below
4. Aided CNC word recognition score (mean of two lists) between 10% and 50%, inclusive (i.e.,  $10\% \leq \text{score} \leq 50\%$ ), in the ear to be implanted
5. Aided CNC word recognition score (mean of two lists) in the contralateral ear equal to, or better than, the ear to be implanted but not more than 70%
6. Willingness to use bimodal stimulation (i.e., a cochlear implant on one ear and a hearing aid on the contralateral ear) through at least 6-months postactivation
7. English spoken as a primary language

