### 8.4 Missing Data

All efforts will be put forth to ensure near complete follow-up, with particular focus on the assessment of the primary outcome and occurrence of adverse events. Regular reminders of subject follow-up due dates will be provided to participating centers to facilitate scheduling of follow-up visits.

Cochlear

In the event a subject is withdrawn prior to the 6-month assessment, the primary analysis of the primary efficacy endpoint will involve imputing the pre-operative CNC word test score for the 6 month CNC word test. This is equivalent to treating each subject with a missing 6 month result as unchanged from baseline. The p-value for the primary efficacy statistical hypothesis test will be calculated using this imputation to understand the impact of missing data on the primary result.

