1.2 Sample Size

A total sample size of 50 evaluable subjects is planned. An allowance of 10% to account for possible attrition is planned such that up to 55 subjects may be recruited into the study and implanted. The planned sample size of 50 subjects will provide adequate power for the primary efficacy endpoint based on a range of assumptions. Power for this test under a variety of assumptions is provided below. Calculations are based on a one-sample t-test at a two-sided 0.05 alpha level.

Table 1. Power for Sample Size of 50 Evaluable Subjects

True Population CNC Word Score Mean Change	True Population CNC Word Score Standard Deviation for Change		
	30%	40%	50%
20%	>99%	93%	79%
25%	>99%	99%	93%

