1.5.2 Supportive Efficacy Analyses

Supportive efficacy analyses will include analysis of individual data for all measures. Individual scores obtained at 6 months will be compared with those obtained, on the same measures preoperatively, based on the binomial model where appropriate (see Thornton and Raffin, 1978) to establish the proportions of those subjects showing improvement, no change, and decrement in performance including:

- On the CNC word measure, most (> 75%) of the subjects at 6 months will score equal to or better in their best unilateral listening condition than they did in the preoperative unilateral aided condition.
- On the AzBio sentences-in-noise measure, most (> 75%) of the subjects at 6 months will score equal to or better in their best unilateral listening condition than they did in the preoperative, unilateral aided condition.
- On the CNC word measure, most (> 75%) of the subjects at 6 months will score equal to or better in their best bilateral listening condition than they did in the preoperative, bilateral aided condition.
- On the AzBio sentences-in-noise measure, most (> 75%) of the subjects at 6 months will score equal to or better in their best bilateral listening condition than they did in the preoperative, bilateral aided condition.

Regression analyses of efficacy parameters will also be done, adjusted for baseline covariates of interest including:

- Age at implantation
- Duration of hearing loss
- Gender

Longitudinal analyses (to 12 months) of efficacy parameters will be analyzed. In addition, change in low-frequency hearing sensitivity (125 to 1000 Hz) for each subject will be documented and ultimately reported as the total number and percentage of subjects who fall within the ranges given in the following table. The impact of any such changes will be assessed in light of overall speech perception outcomes.

Change in low-frequency hearing sensitivity
≤10 dB
>10 dB and ≤20 dB
>20 dB and ≤30 dB
>30 dB

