1.7 Missing Data

All efforts will be put forth to ensure near complete follow-up, with particular focus on the assessment of the primary outcome and occurrence of adverse events. Regular reminders of subject follow-up due dates will be provided to participating centers to facilitate scheduling of follow-up visits.

In the event a subject is withdrawn prior to the 6-month assessment, the primary analysis of the primary efficacy endpoint will involve imputing the pre-operative CNC word test score for the 6 month CNC word test. This is equivalent to treating each subject with a missing 6 month result as unchanged from baseline. The p-value for the primary efficacy statistical hypothesis test will be calculated using this imputation to understand the impact of missing data on the primary result.

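### The promised tipping-point analysis has no method: the section it points to holds only the zero-change imputation that is already the primary analysis

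*SAP*

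**What the plan says.** SAP 1.1 and Protocol 8.1 evaluate the primary endpoints in the ITT population and add, in the same words in both documents: "A tipping point sensitivity analysis will be conducted by the methods described in the missing data section to address any missing data". SAP 1.1 also provides a second look at the endpoint: "A supportive analysis of the primary endpoint will be done in the CC population".

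The section referred to is SAP 1.7, repeated as Protocol 8.4. For a subject withdrawn before the 6-month visit, "the primary analysis of the primary efficacy endpoint will involve imputing the pre-operative CNC word test score for the 6 month CNC word test". Protocol 8.4 explains: "This is equivalent to treating each subject with a missing 6 month result as unchanged from baseline". The section closes by saying that the primary p-value "will be calculated using this imputation to understand the impact of missing data on the primary result". It gives no range of alternative values, shift, worst case, or rule for where the conclusion changes.

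Elsewhere the plan allows for decline. SAP 1.5.2 will report "the proportions of those subjects showing improvement, no change, and decrement in performance" and expects only that more than 75% will score equal or better on unilateral CNC. Protocol 9.0 anticipates that any subject may lose some or all residual hearing in the implanted ear.

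**The concern.** A tipping-point analysis asks how poor the unseen outcomes would have to be before the primary result fails. To answer, it must vary the value given to missing subjects. Here the cross-reference leads to a single fixed value, zero change, which the primary analysis already uses. The one calculation therefore serves as both the primary analysis and the check on it.

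The CC analysis drops missing subjects and so cannot give them a loss. Zero change is also not the lowest possible outcome. The entry rule is "Aided CNC word recognition score (mean of two lists) between 10% and 50%, inclusive", so a subject whose 6-month score is 0 has changed by between -10 and -50 points.

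If the range, step and criterion are left to the analyst, they will be chosen after the results are known, in an open-label, single-arm study with one primary efficacy test.

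**Working it through.** **Inputs**
- 50 evaluable subjects and up to 55 implanted (SAP 1.2: "An allowance of 10% to account for possible attrition is planned"), so 55 - 50 = 5 missing.
- Planning mean change 20 or 25 points; SD of change 30, 40 or 50 (SAP 1.2).
- One-sample t-test on the paired change, one-sided 0.025 (SAP 1.4.1).
- Preoperative CNC 10% to 50% (Protocol 4.1.1). Assumed entry scores of five missing subjects: 10, 20, 30, 40, 50.

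**The plan's own figure.** Power from the noncentral t distribution, df 49, noncentrality (mean/SD) × √50, upper tail 0.025, is 99.6%, 93.4%, 79.2% for mean 20 and 99.99%, 99.1%, 93.4% for mean 25 (SD 30, 40, 50). SAP Table 1 is reproduced in all six cells and is not in dispute.

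**Formula.** With n completers (mean m, SD s), k missing subjects given changes c, and N = n + k:
- S = n·m + Σc
- Q = (n - 1)s² + n·m² + Σc²
- V = (Q - S²/N)/(N - 1)
- t = S/√(N·V), df N - 1

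**Why the CC analysis adds little.** Imputed zeros leave S and Q unchanged. For mean 20, SD 50: S = 50 × 20 = 1,000 and Q = 49 × 2,500 + 50 × 400 = 142,500.
- CC, N = 50: V = (142,500 - 20,000)/49 = 2,500; t = 1,000/√125,000 = 2.828; p = 0.00338.
- Five zeros, N = 55: V = (142,500 - 18,182)/54 = 2,302; t = 1,000/√(55 × 2,302) = 2.810; p = 0.00344.

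**Worst case, planning values observed, 5 of 55 missing.** Every missing 6-month score is set to 0, so the imputed changes are -10, -20, -30, -40, -50. For mean 20, SD 50: S = 1,000 - 150 = 850; Q = 142,500 + 5,500 = 148,000; V = (148,000 - 13,136)/54 = 2,497; t = 850/√(55 × 2,497) = 2.293; p = 0.0129.

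| Mean/SD | One-sided p at these floors |
|---|---|
| 20/30 | 0.0004 |
| 20/40 | 0.0036 |
| 20/50 | 0.0129 |
| 25/30 | <0.0001 |
| 25/40 | 0.0004 |
| 25/50 | 0.0024 |

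No cell exceeds 0.025. The 20/50 cell can be made to fail by more extreme entry scores: p = 0.028 with all five at -50, and p = 0.0251 with four at -50 and one at -35. Nearly all missing subjects would have to enter near the 50% ceiling and then score 0.

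**Narrow passes, 5 of 55 missing.** Fix the zero-imputed p, solve for the observed mean, then lower c in 1-point steps, stopping each subject at minus the entry score.

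| Zero-imputed p | SD | Observed mean | First c with p > 0.025 |
|---|---|---|---|
| 0.020 | 30 | 9.0 | -4 |
| 0.020 | 40 | 11.9 | -6 |
| 0.020 | 50 | 14.9 | -7 |
| 0.010 | 30 | 10.2 | -16 |
| 0.010 | 40 | 13.6 | -23 |
| 0.010 | 50 | 17.0 | -31 |

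**Higher attrition.** Assume 10 of 55 missing, each entry score used twice, and planning values observed in 45 completers. The 20/50 cell has p = 0.0053 at zero change and tips at -22. The 20/40 cell has p = 0.0009 and tips at -45.

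**The case against.** The strongest reply is that the primary analysis already penalises missing subjects: zero change lies 20 to 25 points below the planning mean. At planned attrition the conclusion also survives a score of 0 for every missing subject in all six planning cells, on the assumed spread of entry scores. The cases that tip need an observed mean well below plan, or 10 missing, which is twice the 5 the plan allows for and leaves 45 evaluable against a planned 50. SAP 1.5.2 describes subjects who were tested and says nothing directly about those who were not. A competent statistician would also know how to run a tipping-point analysis.

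All of this stands as a limit on size. It does not supply the missing method. Baseline imputation may be a reasonable primary choice, but it cannot show how far it would have to be wrong.

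A reader might infer that the primary test is invalid, that the result is fragile, or that worsening is ignored. The documents support none of these. The test, alpha and sample size are unaffected, the planning cells are robust at planned attrition, and observed worsening enters both the ITT and CC analyses. Only unobserved worsening is left out.

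**Conclusion.** The concern holds. Both documents promise a sensitivity analysis whose stated method is the primary analysis itself, and no other planned analysis gives a missing subject a loss. This goes beyond missing detail, because following the text literally returns the primary p-value.

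The consequence is modest at planned attrition with planning values observed. It becomes material for a narrow pass, where imputed losses of 4 to 7 points undo a p of 0.020, or for attrition near twice the allowance in the 20/50 and 20/40 cells. It should be corrected, but it does not call the primary analysis into question.

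These sizes rest on assumptions about the number missing, their entry scores and the observed means and SDs; the documents contain no observed data. That the cross-reference leads to no separate method rests on the text alone.

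**What to change.** In SAP 1.7 and Protocol 8.4:

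1. Keep imputation of the preoperative score as the primary analysis, and apply it to every ITT subject with a missing 6-month CNC score. At present one sentence covers subjects withdrawn before the visit and the next covers any missing result.
2. Define the tipping-point analysis separately. For those same subjects, lower the imputed change from 0 in 1-point steps, floored at minus each subject's own preoperative score. One point is one word out of two 50-word lists (Protocol 5.3.2).
3. Rerun the primary test at each step. Report the first value at which one-sided p exceeds 0.025, or state that none does.
4. Report that value beside the distribution of observed changes in completers, so that its plausibility can be judged.

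Other grids would serve; what matters is that one is fixed before results are seen. The cost is a few sentences in each document and, since no entry score exceeds 50%, at most 50 further t-tests. The preoperative scores are already collected, and the primary analysis method, sample size and alpha stay as they are.

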1.5 Additional Statistical Analyses

1.5.1 Analysis of Baseline Characteristics

The baseline characteristics of the study groups will be presented descriptively. Quantitative variables such as age will be presented with mean, standard deviation, median, minimum and maximum. Qualitative variables such as gender will be presented with number with the condition, the sample size, the percentage, and the 95% two-sided exact binomial confidence intervals.

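### The four supportive >75% proportions are planned in completed cases only, so they can overstate benefit if subjects without a 6-month score do worse than completers

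*SAP*

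**What the plan says.** SAP 1.1 defines two populations. ITT is everyone in whom implantation of the CI422 is attempted. The completed cases (CC) are "treated subjects who had follow-up of the primary endpoint at the protocol prescribed time". On use, it says "The primary efficacy and safety endpoints will be evaluated with the ITT population". It adds that effectiveness analyses will also be done in CC, and ends: "Additional analyses will be examined only in the CC population". Protocol 8.1 has the same text.

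The proportions are in SAP 1.5.2, under the heading "1.5 Additional Statistical Analyses". The first, for CNC words, expects that "most (> 75%) of the subjects at 6 months will score equal to or better in their best unilateral listening condition" as in the preoperative unilateral aided condition. The other three repeat this for AzBio unilateral, CNC bilateral and AzBio bilateral. Individual scores are classified as improved, unchanged or decreased, with a binomial model where appropriate.

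SAP 1.7 gives one imputation rule, for the primary efficacy endpoint: the preoperative CNC score replaces the missing 6-month score. It explains: "This is equivalent to treating each subject with a missing 6 month result as unchanged from baseline". Nothing says how a subject without a 6-month score counts in the four proportions. SAP 1.4.2 and 1.4.3 name neither a population nor a missing-data rule for the three secondary tests.

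**The concern.** A reader will take these proportions as the share of implanted adults who end up no worse on each measure. Protocol 9.0 warns that any subject may lose some or all residual hearing in the implanted ear, permanently, so that share bears on the balance of risk and benefit. Under the CC rule, a subject who was implanted and then left is not counted at all, and Protocol 7.2 lists an adverse event among the possible reasons for leaving. A failed implantation attempt is likewise in ITT but would not count as treated. If such subjects do worse than completers, the reported figure is too high, and no other column in the plan shows by how much.

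The obvious repair, moving to ITT with the SAP 1.7 imputation, would make things worse. Zero change is a cautious assumption for a mean improvement. For a criterion that accepts an equal score, it turns every leaver into a success.

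**Working it through.** **Inputs.** 50 evaluable subjects, a 10% attrition allowance and up to 55 implanted (SAP 1.2); criterion strictly above 75% (SAP 1.5.2); CC for additional analyses (SAP 1.1); zero-change rule (SAP 1.7).

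**The plan's own figures.** 50 × 1.10 = 55, as stated. A one-sample t-test with n = 50 and two-sided 0.05 (noncentral t) gives power of 99.6%, 93.4% and 79.2% for a mean change of 20 with SD 30, 40 and 50, and >99.9%, 99.1% and 93.4% for a mean change of 25. All six cells of SAP Table 1 reproduce. Only the 50 and 55 matter for the proportions.

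**Smallest count above 75%.** For n subjects this is the smallest integer greater than 0.75n.
- CC, n = 50: 0.75 × 50 = 37.5, so 38 (38/50 = 76.0%).
- ITT, n = 55, leavers counted as not meeting: 0.75 × 55 = 41.25, so 42 (42/55 = 76.4%). All 42 must come from the 50 completers, and 42/50 = 84%.

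**Counts on which the two disagree, 5 of 55 missing.**

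| Successes | CC (of 50) | ITT, missing = not meeting (of 55) |
|---|---|---|
| 38 | 76.0% | 69.1% |
| 39 | 78.0% | 70.9% |
| 40 | 80.0% | 72.7% |
| 41 | 82.0% | 74.5% |

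With 38 successes among completers, 42 − 38 = 4 of the 5 leavers would have to be successes for the ITT figure to pass. With 41, only 1 would.

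**Other amounts of missing data, at the smallest passing CC count.**

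| Missing of 55 | CC | Same count over 55 |
|---|---|---|
| 0 | 42/55 = 76.4% | 76.4% |
| 1 | 41/54 = 75.9% | 74.5% |
| 2 | 40/53 = 75.5% | 72.7% |
| 3 | 40/52 = 76.9% | 72.7% |
| 5 | 38/50 = 76.0% | 69.1% |
| 8 | 36/47 = 76.6% | 65.5% |

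**Zero-change rule applied to the proportions.** Five leavers become five successes. Then 37 completers suffice, since (37 + 5)/55 = 76.4%, although 37/50 = 74.0% fails in CC. The bar falls below the CC bar.

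**If leavers resemble completers.** At 38/50, five leavers with the same 76% rate add 3.8 expected successes: (38 + 3.8)/55 = 76.0%. CC is then unbiased.

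**Secondary tests, completers versus ITT with five zero changes.** For 50 completers with mean m and SD s, t = m√50/s. Adding five zeros gives mean 50m/55 and variance [49s² + 50m² − 55(50m/55)²]/54. AzBio values are not in the documents, so the CNC power-table values are used as an assumption.
- m = 20, s = 40: t = 3.54 with 50. With 55, the mean is 18.18, the variance (78,400 + 20,000 − 18,182)/54 = 1,485.5, and t = 3.50.
- m = 20, s = 50: 2.83 versus 2.81.
- m = 25, s = 30: 5.89 versus 5.72.

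The completers' mean is 55/50 = 1.10 times the imputed mean, but the SD and n change too, so the t statistic hardly moves.

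**The case against.** The best defence is that nothing depends on these proportions. SAP 1.5.2 calls them supportive. They lie outside the testing sequence in SAP 1.4.3 and have no hypothesis, alpha or success rule. A reader might infer that the study could pass an acceptance criterion because of attrition. The documents do not support that, because they attach no consequence to falling on either side of 75%. This stands.

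Second, the classification compares two observed scores, so a subject without the second cannot be classified. Counting every leaver as not meeting is harsh on, say, a voluntary withdrawal, and is biased downward if leavers resemble completers. This also stands. It is a reason to show both figures, not to show CC alone.

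Third, 5 of 55 is an allowance for possible attrition, not a forecast, and the disagreement appears only for counts near the threshold. That is correct, although one missing subject is enough to flip a borderline count.

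Fourth, a reader might infer that subjects who leave because of harm disappear from the evidence. They do not: the primary efficacy and safety endpoints use ITT, and SAP 1.3.1.1 tabulates adverse events, with exact confidence limits for device- and procedure-related rates.

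Fifth, a reader might infer that the secondary tests are restricted to completers and inflated by 10%. SAP 1.1 does not settle this: saying that effectiveness analyses are *also* done in CC can mean ITT plus CC. The 10% applies to the mean change and does not carry through to the test statistic.

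The defence does not answer the plain reading of SAP 1.1 with the heading of SAP 1.5: these four proportions are planned in completers only, with no count of those left out.

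**Conclusion.** The point holds as a reporting weakness in a descriptive analysis. The CC restriction can bias the four proportions upward, and does so only if subjects without a 6-month score do worse than completers. At the full attrition allowance, 38 to 41 successes fall above 75% in CC and below it over all 55 with leavers counted as not meeting. At 38 successes the possible range over all 55 runs from 69.1% (no leaver succeeds) to 43/55 = 78.2% (all five do), so the lower figure is a conservative bound, not an estimate. The primary efficacy conclusion is unaffected.

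For the secondary tests the finding is an unstated population and missing-data rule. At the assumed CNC values the effect on t is small (for example 3.54 versus 3.50).

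The separate >75% expectation in SAP 1.3.2, for subjects with a marked hearing shift, is not part of this point.

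**What to change.** In SAP 1.1 and 1.5.2, report each of the four proportions twice: in CC, and over the ITT population with a missing 6-month score counted as not meeting the criterion. Show the number missing beside them. State that the zero-change rule in SAP 1.7 does not apply to these proportions, because an unchanged score would count as success.

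In SAP 1.1 and 1.7, state that the three sequential secondary tests use the ITT population with the same preoperative-score imputation as the primary, so that the whole sequence follows one rule. The scores needed are already collected at the preoperative baseline (Protocol 5.4.2.1). Protocol 8.1 and 8.4 repeat the SAP text and should be aligned.

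The cost is some wording, one extra column per table and slightly less favourable figures. No new data are needed.
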